3. INFORMED CONSENT PROCESS

For in-person informed consent, it will take place in a quiet setting and in a manner such that the participant does not feel rushed or pressured. If telephone/video-based informed consent is received, the potential participants will be mailed two paper copies of the informed consent (one to send back to study team and one to keep for their records) and asked to review them prior to the telephone call with study staff.

In both in-person and telephone/video-based informed consent procedures, subjects will be informed about all aspects of the study and asked to read the consent form. The form will be written in simple, easy-to-understand language. We require study staff to review all key aspects of the study verbally. Staff will be provided with a structured checklist for this purpose. As the participant reads each page, they are asked to initial the page and encouraged to ask questions. Prior to signing the document, they will be asked basic questions about the study to ascertain as best as possible if they have understood the requirements of the study, the potential risks, and the potential benefits. A copy of the informed consent will be given to the participant, and the original signed copies will be kept in the participant's file.

4. RISKS AND BENEFITS

All data obtained from participants is considered confidential. Precautions will be taken to protect computerized or electronic data from unauthorized disclosure, tampering, or damage by controlling access to the computers and files that hold this information. Access to computer files will only be obtained through passwords and will

only be accessed by IRB-authorized research study personnel. Only authorized research study personnel will have permission to examine computer records to identify which patients are eligible to approach. Analysis of data will be performed at The Ohio State University by the study PI and with assistance from [name] (OSU College of Medicine). Whereas no assurance can be made to an individual participant that he or she will personally benefit from such research, the experience should be beneficial. The risks compared to the potential benefits are minimal to the individual research participant and virtually nonexistent to others or society in general. More information about the risks and benefits are on pages 8-10.

III. STUDY PROCEDURES

1. WHAT WILL BE DONE

The study's overall goal is to recruit 70 older cancer survivors to examine the feasibility and preliminary efficacy of a 12-week online dietary and resistance training intervention to improve their physical function through increased protein consumption, healthy eating, and resistance training.

[figure not shown]
2. HOW IT WILL BE DONE

The E-PROOF intervention core content is from publicly available, pre-existing educational content provided by the NIA, NCI, American Cancer Society, American College of Sports Medicine (ACSM), and OSUCCC. The dietary core content includes: 1) recommended amount and sources of protein intake; 2) healthy eating as an OCS; 3) protein intake benefits; and 4) importance of maintaining physical function through diet. The resistance training intervention core content includes: 1) recommended frequency and resistance training exercises; 2) resistance training benefits; 3) different muscle groups; and 4) the importance of maintaining physical function through resistance training. Intervention participants will also have the option of attending Zoom®-based social hours (held at 7-8pm EST, 1 day/week, weeks 3, 6, 9) to share their thoughts and experiences with each other. Informed design was used for intervention development by reviewing relevant evidence; replicating prior successful intervention elements from the PI and co-Is and; incorporating feedback from the Cancer and Aging Research Group's patient advocacy group (see Letter of Support).

Randomization and Baseline Assessment: Subjects will be block randomized by the number of physical function limitations measured by the PFSS.⁴⁰ At the in-person visits at baseline and end-of-study, study staff will measure the physical function (SPPB), muscle strength (handgrip, SPPB), height, weight, and waist circumference of all participants (intervention and control). The Research Electronic Data Capture (REDCap) secure platform^{41,42} will be used for baseline questionnaire data collection, which will assess dietary quality (DHQIII), self-reported exercise, HRQoL, self-efficacy, and demographic and clinical information. After data collection, the research assistant will show intervention participants how to access the REDCap-based logs and enter their weekly dietary intake and exercise adherence. At the end of the baseline visit, intervention participants will receive a binder with printed educational materials on increasing dietary protein, healthy eating, and resistance training to preserve or rebuild lean body mass as a reference tool. Resistance bands (three levels of Thera-bands®), and resistance band exercise guidelines (exercises by muscle group, proper form, how to rate difficulty) will be distributed to intervention participants.

Intervention Participants. Participants randomized to the intervention group (n=35) will be paired after the baseline assessment with a RD and ES for the duration of the 12-week intervention (**Figure 1**). The diet and resistance training intervention will be tailored to each participant in the intervention group based on the information collected during their baseline visit.

Figure 1. Study schema

Nutritional counseling: Within 1 week of the baseline visit, a RD will review the DHQIII results and create a tailored dietary plan focusing on protein intake and healthy eating for each intervention participant. At weeks 1, 3, 5, 7, 9, and 11, the RD will provide one-on-one, online (Zoom®, FaceTime®) nutritional counseling to the intervention participants. During the biweekly online 30-minute visits, the RD, guided by elements in behavior change theories, will review and check on their progress toward increased protein intake and healthy eating, use motivational interviewing strategies to support the participants' progress, provide reinforcement, explore strategies to overcome barriers, field questions, and establish tailored goals. Counseling will consist of education to stimulate sufficient protein- and energy intake using regular food, based on the current American Cancer Society nutrition guidelines for cancer survivors⁴³ and DGAs for protein and energy for adults aged ≥60 (5-6.5 oz. eq/day based on 1,600-2,600 calories/day).⁴⁴ Counseling of these protein targets will account for variability in body weight.⁴⁵⁻⁴⁷ Due to physiological limit of protein synthetic capacity, spread feeding of proteins over the day is preferred and participants will be advised to consume 25-30 grams of proteins per meal.¹⁸ After the counseling session for weeks 1, 5, and 9, the RD will email/mail participants menus, snack ideas, and recipes focused on protein and healthy eating. Participants will be encouraged to record their weekly dietary intake in their REDCap-based log to practice self-monitoring, provide motivation, and facilitate recall and reflection during nutritional counseling sessions. RDs will access these online entries to review participants' protein and overall dietary intake and provide recommendations during counseling.

Resistance training counseling: For the first 6 weeks, the ES will host weekly, one-on-one, 30-minute, online resistance training sessions for the intervention group, using a progression model.⁴⁸ After week 6, the resistance training sessions will taper, and be held biweekly at weeks 8, 10, and 12. Based on behavior change models, at the beginning of all sessions, the ES will review progress toward increased resistance training, and support progress and strategies to overcome barriers through motivational interviewing. In each training session, the ES will provide education, then lead participants through a 5-minute warm-up, followed by a series of whole-body exercises (each major muscle group) performed at each session, and a 5-minute cool-down. The training is based on a co-I's ([name]) expertise in exercise interventions,⁴⁹⁻⁵¹ the ACSM exercise guidelines for cancer survivors,⁵² and ACSM recommendations for progressive resistance training for older adults⁵³ consisting of 1-3 sets of 8-10 exercises with 8-12 repetitions with a 1-2 min rest between sets. Participants will be encouraged to complete these exercises two more times/week, totaling three sessions/week, and record their weekly resistance trainings in the REDCap platform (same weekly log as dietary intake). The diary will ask participants if they exercised (yes/no), type of exercise (i.e., resistance training, walking), intensity (mild/moderate/strenuous) and the time spent exercising for each day of the week. Diaries will be used by the ES to assess exercise adherence and to progress the exercise program during training sessions. Participants will be encouraged to refer to their educational materials for guidance between synchronous resistance training sessions.

Enhanced Control Participants. Participants randomized to the enhanced control group (n=35) will not receive online nutritional or resistance training education or counseling. Control participants will take part in three in-

person assessments (baseline, end-of-study, 3-month follow-up) with study staff and receive printed materials (NCI's "Facing Forward: Life After Cancer Treatment") pertaining to general cancer survivorship.

Follow-up. Three months after the 12-week intervention, all participants will return for an in-person assessment by study staff of physical function, muscle strength, and HRQoL. This information is essential to understanding the sustained impact of this intervention and trajectories of physical function among OCS.

3. *TIMELINE*

We will work with cancer clinic leadership, clinicians, and clinic staff to coordinate recruitment to ensure that clinic flow is not disrupted. The Clinical Research Coordinator, TBN, will serve as a central point of contact and will assist with these activities. Throughout the course of the study period, [name] will hold regular staff meetings to discuss recruitment, and to address any issues that occur on a case-by-case and clinic-by-clinic basis. The Clinical Research Coordinator will directly supervise the day-to-day progress of all study activities. We estimate a large number (n~150) of potentially eligible patients on an average weekday at the OSUCCC, with a limiting factors being workforce, clinic flow, and participation rates. We anticipate that we can feasibly enroll an average of 2 patients per day over 9 months of recruitment and reach our recruitment goal of 70 participants.

Figure 2. Timeline and Work Plan

	Year 1				Year 2			
Study Quarters (over 2 years)	1	2	3	4	1	2	3	4
Participant Recruitment								
Recruitment of 70 older cancer survivors								
Aim 1: Determine Feasibility and Acceptability of Intervention								
Implementation of a 12-week online, tailored nutritional and resistance training counseling intervention								
Measurement of accrual, retention, and adherence rates								
Analysis of participant intervention evaluation								
Aim 2: Examine Efficacy of Intervention								
Measurement of physical function, muscle strength, and height, weight, and waist circumference at baseline and 12 weeks								
Measurement of diet quality, exercise, health-related quality of life, self-efficacy, and demographic and clinical information through REDCap-based questionnaires at baseline and 12 weeks								
Analysis of change in physical function, muscle strength, and height, weight, and waist circumference from baseline to 12 weeks								
Analysis of change in diet quality, exercise, health-related quality of life, self-efficacy, and demographic and clinical information from baseline to 12 weeks								
Examine Maintenance of Intervention								
Measurement of physical function, muscle strength, and health-related quality of life at 3-month follow-up								
Analysis of change baseline and end-of-study (6 months) in physical function, muscle strength, and health-related quality of life								
Integration and Dissemination Activities								
Project meetings, monitoring, and fidelity checks								
Prepare abstracts, manuscripts, and presentations								
Preparation and submission of next-step grant application								

DATA COLLECTION AND MANAGEMENT PROCESS

4. DATA TO BE COLLECTED

We are collecting data using all validated measures. Our main outcome is physical function which will be measured by The physical performance assessment, Short Physical Performance Battery (SPPB)⁵⁴, will measure physical function at baseline, end-of-study, and follow-up. The SPPB includes three lower extremity physical performance measures (standing balance, five consecutive chair rises, 4-meter gait walk at usual pace) to assess lower extremity strength.

Secondary outcomes will be:

- *Acceptability.* At end-of-study, intervention group participants will complete a 5-item, Likert-scale questionnaire, with written comments, regarding their preferences for receiving education and counseling, successes and challenges, program satisfaction, and suggestions for improvement.
- *Feasibility.* Intervention feasibility will be measured by rates of accrual, retention, and adherence at baseline, end-of-study, and 3-month follow-up. Recruitment rate is based on Consolidated Standards of Reporting Trials criteria⁵⁵ that includes eligible consented individuals and eligible non-consented individuals with non-recruitment reasons documented. Process information (number/duration of video visits) will be recorded.
- *Muscle Strength.* Handgrip strength will be measured at baseline, end-of-study, and follow-up in both hands using a hydraulic grip strength dynamometer (Jamar Model 7498).
- *Dietary Quality.* Protein intake and dietary quality will be assessed at baseline and end-of-study by the National Cancer Institute's DHQIII.⁵⁶
- *Resistance exercise.* Self-reported resistance exercise will be assessed using the revised version of The Godin-Shephard Leisure-Time Exercise Questionnaire (LTEQ) modified to specifically capture self-reported resistance exercise participation.
- *HRQoL.* RAND-36 Health Status Measure⁵⁷ is comprised of 8 subscales assessing multiple aspects of HRQoL. Physical and mental component summaries are created. All scores range from 0-100, with 100 as the highest.
- *Self-efficacy.* Baseline and end-of-study self-efficacy for diet and resistance training will be measured by: "How sure are you that you could do exercises to make your body stronger for 15 minutes, 3 days a week?" and "How sure are you that you could improve your diet?"
- *Self-regulation.* Baseline and end-of-study self-regulation for diet and exercise will be measured by the 12-item Dietary Self-Regulation Scale⁵⁸ and the 12-item Exercise Self-Regulation Scale⁵⁹.
- *Technology competency.* The 8-item eHealth Literacy Scale (eHEALS)⁶⁰ will measure knowledge, comfort, and perceived skills of engaging in eHealth at baseline and end-of-study. A 5-point Likert scale will be used.
- *Anthropometry.* Body weight, height, and waist circumference will be collected at baseline and end-of-study.
- *Demographic and Clinical Information.* Participants' age, race, ethnicity, gender, education, income, marital status, insurance status, cancer diagnosis, stage at diagnosis, time since diagnosis, treatments received (e.g., chemotherapy, radiation) and comorbidities will be collected at baseline and updated at end-of-study.

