Aim 1: Determine the feasibility and acceptability of implementing a 12-week online dietary and resistance training randomized trial with 70 older cancer survivors. This aim will be accomplished by collecting detailed process data, which allows the assessment of accrual, retention, and adherence. Our hypothesis is that we will recruit (within 9 months) 70 OCS, retain $\geq 80\%$ of the sample, and maintain $\geq 80\%$ adherence to the intervention.

Aim 2: Examine the preliminary efficacy of this 12-week online dietary and resistance training intervention with the intervention participants. Registered dietitians and exercise scientists will provide these participants with tailored dietary and resistance training recommendations, counseling, and educational materials. Our hypothesis is that intervention participants will experience statistically significant, clinically meaningful improvements in physical function and associated health outcomes (i.e., muscle strength, dietary quality, HRQoL, self-efficacy,

weight management) after the 12-week dietary and resistance training intervention and at a 3-month post-intervention follow-up.

METHODS

I. STUDY DESIGN

We will examine the feasibility and preliminary efficacy of a 12-week online dietary and resistance training intervention to improve the physical function of OCS through increased protein consumption, healthy eating, and resistance training. In this pilot randomized controlled trial, participants (n=70) will be randomized to one of the two groups: experimental (online counseling, menus, educational materials) and enhanced control (passive educational materials). We will examine the intervention effects on physical function and associated health outcomes during the 12-week period between the experimental and control group.

II. PARTICIPANT SELECTION

1. *ELIGIBILITY CRITERIA*

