4. STUDY TERMINATION PROCEDURES

Participants will be informed that they can stop participating at any time with no penalties to them. If participants decide to stop being in the study, their surveys will be deleted from the REDCap system. However, if participants only choose to answer certain questions without explicitly stating a desire to no longer participate, survey data for those answered questions will be stored.

V. STATISTICAL METHODS

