2. DATA ANALYSIS PLAN

Aim 1: The feasibility of implementing a 12-week online diet and resistance training intervention with OCS will be determined by the study accrual rate, retention rate, and adherence rate. The study accrual rate will be calculated by dividing the number of potential participants that passed screening by the total number of participants started in the study after appropriate informed consent procedures. The recruitment goal is set at 70 participants recruited over a 9-month period. Retention rate will be calculated by dividing the total number of participants initiated by total number of participants in the study at baseline and 12 weeks (end-of-study). Retention goal for this trial is 80%. If 80% (56/70) of participants are retained at end-of-study, the retention goal for this trial will be achieved. Previous studies by the study team had similar recruitment and retention rates of older participants.⁷¹⁻⁷³ We are confident in our ability to recruit and retain the study participants necessary to conduct the proposed study. Participants will be determined to be adherent if they attend ≥80% of the intervention sessions (in-person meetings with study staff and online intervention sessions).^{71,74,75} Overall adherence and

retention rates and associated 95% confidence intervals will be reported at baseline, end-of-study, and 3-month follow-up.

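### Acceptability is asked only at end-of-study, and nobody who leaves the study earlier is asked for views or reasons, so the Aim 1 acceptability result may be overstated

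*Combined protocol and SAP*

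**What the plan says.** The Specific Aims state Aim 1 as "Determine the feasibility and acceptability of implementing a 12-week online dietary and resistance training randomized trial". The acceptability measure appears once, among the secondary outcomes in Data to be collected: "At end-of-study, intervention group participants will complete a 5-item, Likert-scale questionnaire, with written comments". It covers preferences, what went well or badly, satisfaction and ideas for improvement. The Data collection timeline places end-of-study at 12 weeks.

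Four other places bear on who can answer:

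- **Arm size** (How it will be done): "Participants randomized to the intervention group (n=35) will be paired after the baseline assessment".
- **Tolerated loss** (Data analysis plan, Aim 1): "If 80% (56/70) of participants are retained at end-of-study, the retention goal for this trial will be achieved".
- **Reasons recorded** (Data to be collected, Feasibility): the recruitment rate includes "eligible non-consented individuals with non-recruitment reasons documented". No matching provision exists for people who join and later leave.
- **Data from leavers** (Study termination procedures): "If participants decide to stop being in the study, their surveys will be deleted from the REDCap system".

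The Aim 1 analysis says that feasibility "will be determined by the study accrual rate, retention rate, and adherence rate". For acceptability it gives no threshold, summary statistic, denominator or rule for non-response. Figure 2 lists an analysis of the participants' evaluation without a method.

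**The concern.** A form given once at week 12 can be answered only by people still in the study then. Those who withdrew because of the sessions, the weekly logs or the technology would be absent, and they are the people whose opinion could differ most from that of the others. The plan records why eligible people declined to join, but not why participants left.

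This pilot is meant to feed a next-step grant application, which Figure 2 lists. The acceptability answers and written comments are its main source for improving the programme. If they come only from those who stayed, the next trial may be planned on too favourable a picture, and the most useful criticism is lost. It cannot be recovered later. This gap is distinct from the deletion of surveys already collected: ending deletion would not help here, because leavers are never given the form.

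**Working it through.** **Inputs from the documents.** 35 allocated to the intervention; 70 in total; retention goal 56/70; one acceptability form at end-of-study.

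**Inputs not in the documents (assumptions).** A satisfied/not-satisfied cut on the form; the share of respondents satisfied, pC, varied over 80% to 100%; the share of leavers satisfied, pL, varied over 0% to 50%, and also set equal to pC. Everyone still in the study is assumed to answer.

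**Step 1: reproduce the plan's figure.** 56/70 = 0.80, as stated. Tolerated losses are 70 − 56 = 14.

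**Step 2: number unasked in the intervention arm, m.**
- Same rate in this arm: 0.80 × 35 = 28 answer, so m = 35 − 28 = 7, which is 7/35 = 20%.
- All tolerated losses in this arm and none in control: 35 − 14 = 21 answer, so m = 14, which is 14/35 = 40%.

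**Step 3: overstatement.** The form gives pC. The figure for all 35 is [(35 − m) × pC + m × pL]/35. The difference is

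overstatement = (m/35) × (pC − pL).

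Its maximum is m/35, reached when all respondents and no leavers are satisfied: 20 points at m = 7 and 40 points at m = 14.

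| m | pC | pL = 0% | pL = 25% | pL = 50% | pL = pC |
|---|---|---|---|---|---|
| 7 | 80% | 16 | 11 | 6 | 0 |
| 7 | 90% | 18 | 13 | 8 | 0 |
| 7 | 100% | 20 | 15 | 10 | 0 |
| 14 | 80% | 32 | 22 | 12 | 0 |
| 14 | 90% | 36 | 26 | 16 | 0 |
| 14 | 100% | 40 | 30 | 20 | 0 |

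Entries are percentage points. For example, at m = 7, pC = 90% and pL = 0%: (7/35) × 0.90 = 0.18, so 90% would be reported against 72% for all 35.

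**Step 4: direction.** The sign depends on pC − pL. If leavers were more satisfied, say pL = 100% with pC = 90%, the result is (7/35) × (−0.10) = −0.02, an understatement of 2 points. With m = 0 there is no difference.

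**Step 5: mean score instead of a percentage.** The same formula applies. Assuming items scored 1 to 5, means of 4.5 for respondents and 2 for leavers give (7/35) × 2.5 = 0.5 of a scale point at m = 7, and 1.0 at m = 14.

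**The case against.** A reader might infer that the acceptability result is biased upward as a matter of fact. The documents do not support that. The bias requires that intervention participants leave and that leavers are less satisfied, and the protocol has no satisfaction data. In people aged 65 or over with a history of cancer, leaving for health or practical reasons is quite possible. This objection stands: upward is the expected direction, not a demonstrated one.

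A reader might also infer that leavers vanish from Aim 1. They do not. They count against retention, and missed sessions count against adherence; both rates are reported with 95% confidence intervals beside the questionnaire. What is missing is leavers' opinions and reasons. Retention and adherence cannot supply these, because they do not separate an unacceptable programme from an unrelated cause.

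Nor does the text restrict the form to people who finished the programme. It says intervention group participants, so someone who stops the sessions but stays in the study can be surveyed under the present wording. The gap is firm only for those who leave the study.

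Three further points are fair. The 80% is a goal, not a forecast of loss. The plan defines no satisfied/not-satisfied cut, so any percentage is illustrative. Barriers are also discussed in counselling, and the weekly logs are used to spot difficulties, so early problems are not wholly invisible. None of these sources is specified as an acceptability measure, and none provides the answers or the reasons of someone who has left.

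**Conclusion.** The point holds in a limited form. Acceptability is a named part of Aim 1, measured once, with no provision for those who leave earlier, so the result may overstate acceptability among those allocated. The ceiling is 20 percentage points if this arm just meets 80% retention. It is 40 points in the extreme case that all 14 tolerated losses fall in this arm. These ceilings depend only on the number unasked; the smaller values in the table rest on assumed satisfaction rates.

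It would be going too far to conclude that Aim 1 fails or that a stated success criterion is compromised. Acceptability has no threshold, so none would flip, and the SPPB analysis is untouched. What suffers is the interpretation of the acceptability result and its use in planning the next trial. This is a worthwhile low-cost improvement.

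**What to change.** 1. **Data to be collected, Acceptability.** Offer the same five items, voluntarily and with the reason for leaving, to each intervention participant at the time of stopping. Offer them at week 12 to all others allocated to the intervention, stating explicitly that this includes those who stopped sessions but remain in the study.
2. **Data analysis plan, Aim 1.** Report the number of respondents out of the 35 allocated. If a satisfied/not-satisfied summary is used, define the cut beforehand and show simple bounds, with non-respondents counted once as not satisfied and once as satisfied.
3. **Study termination procedures and the matching consent wording.** State that exit answers given voluntarily are kept. Under the present rule an exit form held in REDCap would be deleted for anyone who decides to stop, which would defeat the first change.

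The cost is a few sentences of amendment and about seven extra short forms at the retention goal, handled by existing staff on the existing platform. Some leavers will decline, so the gap will narrow but not close. The reported figure may be less favourable.
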